13 FIN	ANCE AND PUBLICATION POLICY	3
	ANCE AND PUBLICATION POLICY	
13.1		3
13.1 13.2	Finance23	3 3
13.1 13.2 14 INC	Finance	3 3 3

SIGNATURE PAGE

Chief Investigator Agreement

The clinical study as detailed within this research protocol (Version 3.0, dated 18th March 2019, or any subsequent amendments will be conducted in accordance with the Research Governance Framework for Health & Social Care (2005), the World Medical Association Declaration of Helsinki (1996) and the current applicable regulatory requirements and any subsequent amendments of the appropriate regulations.

Chief Investigator Name: [name]

Chief Investigator Site: King's College London

STUDY SYNOPSIS

Full Title	cervical screening without a speculum to increase uptake in lapsed attenders aged 50-64					
Short Title	Cervical screening without a speculum for women aged 50-64.					
Protocol Version	3.0 dated 18 th March 2019					
number and Date						
Study Duration	14 months					
Study population	Women aged 50-64 who are cervical screening lapsed attenders (at least 12 months overdue but screened at least once in the last 15 years)					
Study Design	A cross-sectional pilot study in 10-12 GP practices in the Barts NHS Health catchment area.					
	Eligible women will be randomised (1:1) to either:					
	A. Intervention arm - A letter offering the choice of:					
	 (i) Booking an appointment with their GP or nurse for a non-speculum clinician sample or, (ii) Ordering a self-sampling kit 					
	OR					
	B. Control arm – Usual care (cervical screening reminder letter)					
Sponsor/Co-sponsors	Kings College London					
Chief Investigator	[name]					
REC number	18/LO/1175					
Aim	To assess the feasibility and acceptability of non-speculum sampling approaches for HPV testing in lapsed attenders aged 50-64					
Number of Subjects	Intervention arm (n=350)					
	Control arm (n=350)					
Main Inclusion Criteria	Women aged 50-64 who are eligible for cervical screening and are at least 12 months overdue but have attended at least once in the past 15 years according to their GP records (i.e. lapsed attenders at least 1 year overdue screening).					
Statistical Methodology and Analysis	We will calculate summary statistics for groups of interest (e.g. the proportion of women who have a non-speculum test (taken by a clinician or return a self-sample). A descriptive analysis of questionnaire data will be used to assess acceptability of each approach, swab-taker experiences, patients' future screening preferences and intention to take part again in the future if invited.					

GLOSSARY OF TERMS AND ABBREVIATIONS

ASR	Annual Safety Report						
CCG	Clinical Commissioning Group						
CI	Chief Investigator						
CIN	Cervical Intraepithelial Neoplasia						
CIN 2+	High-grade disease / Cervical Intraepithelial Neoplasia 2 or worse						
EMIS	Egton Medical Information Systems						
GAfREC	Governance Arrangements for NHS Research Ethics Committees						
GP	General Practitioner						
HCA	Health Care Assistant						
HCP	Health Care Practitioner						
HPV	Human Papillomavirus						
HPV Triage	The process whereby HR-HPV testing is used to determine whether						
	women with low grade cervical abnormalities require further						
	assessment.						
HR-HPV	High-risk HPV						
ICF	Informed Consent Form						
ISRCTN	International Standard Randomised Controlled Trial Number						
KCL	King's College London						
LBC	Liquid Based Cytology						
NHAIS	National Health Authority Information System						
NHSCSP	National Health Service Cervical Screening Programme						
NHS R&D	National Health Service Research & Development						
PI	Principal Investigator						
PIS	Patient Information Sheet						
QMUL	Queen Mary University of London						
Subject	An individual who takes part in a clinical trial						
REC	Research Ethics Committee						
SDV	Source Document Verification						
SOP	Standard Operating Procedure						
SS	Self-Sampling						

1 INTRODUCTION

Annually, around 20% of new cervical cancer diagnoses in the UK occur in women aged 65 and over [1] and around 50% of the deaths.[2] Most of these cases occur in women who are not adequately screened when aged 50-64.[3] Women aged 65 who have had regular screening (i.e. 3 consecutive negatives) have a much lower risk of developing disease compared to those who have not been screened between ages 50-64.[3] Additionally, the consistent fall in screening coverage [the rates of cervical cancer in older women are likely to rise] of the NHS Cervical Screening Programme (NHSCSP) is a cause for concern. As of March 2017, coverage was 74.5% of women aged 50–64 compared with 78% in 2011.[4] This falling coverage among older women, coupled with the projected increase in life expectancy, [5] means there is clear need to increase screening coverage in older women. [4]

Cervical screening non-attendance in older women is associated with perceptions of low risk of cervical cancer and low levels of knowledge about cervical screening.[6] However, a key barrier, in older women, is the speculum examination due to increased discomfort from musculoskeletal problems and vaginal atrophy [7] [8].

Almost all cervical cancers are attributable to persistent infection with human papillomavirus (HPV),[9, 10] with around 70% of cervical cancer cases caused by HPV16 and HPV18.[11] Advances in molecular biology techniques has enabled testing for high-risk HPV infection to be used as a form of cervical screening. HPV testing is better than cytology (previously known as a 'smear test') at detecting high-grade disease, [12] and HPV primary screening will replace cytology in England in 2019.[13]

HPV testing has introduced the possibility of new cervical screening approaches that are likely to be more acceptable to older women, as sampling from the cervix is not necessary. HPV testing on self-collected samples has the potential to overcome most barriers to conventional screening.[14-16] Women can take the sample themselves in private without needing to be examined, at a time and place of their choosing. Self-samples are slightly inferior to clinician HPV samples (similar specificity but lower sensitivity to high-grade CIN disease) [17] but are roughly on par with good quality cytology on clinician samples.[17] Therefore, self-sampling (SS) is not recommended for primary screening but is an appealing approach to improving uptake in non-attenders. Self-sampling is already being offered to non-attenders in some countries such as The Netherlands, Australia [18] and Italy. The main drawbacks are that self-sampling is slightly less sensitive than clinician-collected HPV samples to CIN2+ [19] and many women worry about not taking a good quality sample. [20-23]

HPV testing on clinician-collected vaginal samples without a speculum is another possibility. Although test performance is likely to be similar to self-sampling it may be more appealing to women who want the reassurance of a clinician-taken sample without the discomfort. Unlike self-sampling, the dialogue between women and screener is maintained. Findings from a recent qualitative study suggest that non-speculum clinician sampling for cervical screening could be an appealing option for older women, particularly for those who may have been put off screening by the speculum examination.[7]. In this study we will offer lapsed attenders (i.e. at least 12 months overdue but have attended at least once in the past 15 years) a choice of non-speculum clinician sampling or self-sampling. The results will provide some evidence on what approach may be effective in increasing screening uptake in non-attenders. Focusing on lapsed attenders as opposed to non-attenders is likely to be more effective for this study as women who have never attended screening by age 50 are likely to be entrenched in their decision to not attend [8] (regardless of what test is offered). This novel approach could be an excellent way of attracting women (who stopped when it became uncomfortable) back to the screening programme.

This study is the final in a series of studies which are part of a larger project looking at the acceptability, test performance and feasibility of HPV testing on non-speculum clinical collected samples in older women for cervical screening. The first study comprised of focus groups in women aged 50-64 and found that non-speculum clinician sampling would be welcomed by both cervical screening non-attenders and by women with a dislike of the speculum. The second study was a cross-sectional study in GP primary care and colposcopy to assess the test performance and (actual) acceptability of non-speculum clinician samples for HPV testing. This study, the final component of the project, is a pilot study which aims to assess the feasibility, acceptability and experiences of non-speculum approaches to HPV testing in the target population (lapsed attenders aged 50-64).

2 STUDY AIM, OBJECTIVES AND ENDPOINTS

2.1 Aim

To assess the feasibility and acceptability of non-speculum sampling approaches for HPV testing in lapsed attenders aged 50-64.

2.2 Objectives

Primary Objective	Endpoint
To estimate the effect of offering non-speculum	Proportion of women screened at 4
sampling to lapsed attenders aged 50-64 on	months from randomisation
cervical screening uptake	(according to GP records) in the
	intervention (non-speculum) vs control
	arm (standard screening).

2.3 Secondary objectives

Secondary objectives	Endpoints
To assess whether any increase on uptake	Coverage at 12 months from
observed at 4 months is maintained at 12 months	randomisation (using GP records) in
(i.e. long term cervical screening coverage).	each arm.
To assess the acceptability of non-speculum	A descriptive analysis of patient
sampling approaches for cervical screening in	questionnaire data.
among women aged 50-64 who are lapsed	
attenders.	
To assess the acceptability of clinician-sampling	The proportion of women who undergo
without a speculum versus self-sampling in lapsed	clinician-taken sampling without a
attenders aged 50-64.	speculum versus the proportion who
	request and return a self-sample.
To assess the feasibility of offering non-speculum	The proportion of eligible women who
approaches for cervical screening in lapsed	test HPV positive and
attenders aged 50-64	a) attend for follow up (cytology or
	colposcopy) within 6 months of
	testing HPV positive on a non-
	speculum sample and
	b) who are treated for CIN2+
To assess the acceptability of non-speculum	A descriptive analysis of swab-taker
sampling for cervical screening among the clinical	questionnaire data.
staff who took non-speculum samples from eligible	
women at GP practices participating in this study.	

3 STUDY POPULATION

3.1 Inclusion Criterion

1. Women aged 50-64 who are eligible for cervical screening who are at least 12 months overdue but have been screened at least once in the past 15 years according to their GP records (i.e. lapsed attenders at least 1 year overdue screening).

3.2 Exclusion Criterion

1. Women unable to provide informed consent.

4 STUDY DESIGN

4.1 Overall design

This is a pilot study in primary care which will involve 10-12 GP practices within the Barts Health Catchment area. Eligible women will be randomised (1:1) to:

- A. Intervention arm A letter offering the choice between two different non-speculum sampling tests for cervical screening:
 - i. Booking an appointment with their GP or nurse for a non-speculum clinician sample or
 - ii. Ordering a self-sampling kit

OR

B. Control arm - Usual care - cervical screening reminder letter

All GP practices in the Barts Health catchment area use Egton Medical Information Systems (EMIS) web for electronic patient records. EMIS web has built-in search, alert and template functions which will be used to identify eligible women.

4.2 Intervention arm

Women who have a non-speculum clinician collected sample

Women randomised to the intervention arm who choose to have a non-speculum vaginal sample by their GP or nurse will contact their GP practice to book an appointment where they will have the sample taken. Depending on the preferences of the GP practice, women will be able to book appointments in at least one of the following ways; by calling the practice (an EMIS alert will be set up to prompt the reception staff about the study), online via EMIS Web 'Patient Access' and by text messaging.

Acceptability questionnaire

Clinical staff who take non-speculum study samples at participating GP practices will be asked to complete a short questionnaire to assess the acceptability of non-speculum sampling. These data will provide information on the practical use of non-speculum sampling and barriers and facilitators to future implementation. (See section 5.8 for further details).

Women who return a self-sample

Women who are randomised to the intervention arm and choose to order a self-sampling kit will be able to do so either by returning a form (included with a freepost envelope in the mailout) or by phone. The kit will consist of a participant information leaflet, a flocked swab (Copan FLOQswab[™]) with an instruction leaflet explaining (written and pictorial) step by step how to collect a sample, a laboratory request/ consent form, a HPV information leaflet, a study questionnaire and a freepost return envelope. The participant information leaflet will inform the women about the possible results of the self-sample.

Both non-speculum clinician collected samples and self-samples will be sent to the Barts Health NHS Trust cytology laboratory where HPV testing will be performed. (See section 6.1 for further details)

Results will be obtained from the laboratory, by the study team (with the women's consent) (see section 9.2 Data Collection)

Participants will also be asked to complete a short questionnaire to assess the acceptability of non-speculum sampling (non-speculum clinician sampling and self-testing) and future screening preferences. (See section 5.7 for further details).

4.3 Control arm (usual care)

Women who are randomised to the control arm will receive the usual cervical screening reminder letter.

4.4 Study Schematic

5 STUDY PROCEDURES

5.1 Identifying and inviting eligible women

Eligible women will be identified using an electronic search of EMIS Web (the GP record software system). The search will be pre-written by the study team and will be carried out by GP practice administrative staff on an agreed census date. Eligible women will be randomised by the GP practice using computer-generated random numbers (provided by the study team) in a ratio of 1:1 to either the intervention or control arm (see section 5.2). GP practices will send women who are randomised to the intervention arm the study documentation (invitation letter, patient information leaflet and HPV information sheet) via the post. Women who are randomised to the control arm will receive their usual cervical screening reminder letter from the screening programme.

5.2 Participant enrolment

Participant enrolment (i.e. randomisation) will be recorded in women's GP record with the allocation. The list of eligible women randomised to the study (with allocation) will be retained at the GP practice and pseudonymised copy will be kept in the investigator site file.

5.3 Informed Consent Procedures

5.3.1 Women randomised to the intervention arm

Women who are randomised to the intervention arm will receive the patient information sheet and an information leaflet on HPV with their study invitation letter.

Women who have a non-speculum clinician collected sample

For women who opt to have a non-speculum clinician-collected sample at their GP practice, the sample-taker will explain the study and obtain written consent prior to the study sample being taken.

Women who return a self-sample

For women who choose to self-collect a sample, consent will be implicit by return of a selfsample along with the laboratory request/consent form which is included in the kit. This form will contain the women's details (to identify the women) and statements detailing precisely what the study involves and what they are agreeing to by returning a self-sample (e.g. regarding permission for the study team to access to medical record data).

5.3.2 Women randomised to usual care (control group)

Women who are randomised to usual care (control group) will not provide consent for the study. Only anonymous aggregate data will be collected for these women.

5.4 Participant withdrawal

In the event that a patient withdraws their consent from the study all samples and data collected up to that date will be used in the study but no further data will be collected.

5.5 Clinical management & follow-up

Study HPV results will be mailed by the study team to the women and their GP. Women who test HPV negative will be advised in their results letter that they are not required to do anything further for the study. As we are unable to record non-speculum HPV samples in the national cervical screening database, women who test HPV negative on a non-speculum sample will continue to receive the usual smear reminder letters (i.e. will remain on normal recall).

Women who test HPV positive will be advised in their results letter to have a cervical cytology test (i.e. conventional cervical screening with liquid based cytology) in a primary care clinic (e.g. GP surgery or family planning clinic). These women will be managed according to their cytology results as per routine clinical care under the NHS Cervical Screening Programme (CSP). Self-sampling studies have found that most (~80%) women who test HPV positive attend follow-up cytology.[6, 10, 15-17]

As an additional safety net, women who test HPV positive on a non-speculum sample who have not had a follow-up test by the end of the study will be invited to a study colposcopy clinic.

All women who are randomised in the study will be passively followed up for 12 months to obtain data on cervical cytology tests and histology results. Only anonymous aggregate data will be collected for women in the control arm or women in the intervention arm who do not have a study sample (i.e. not consented to the study). GP records will be used for this purpose.

5.6 Inadequate samples

Women whose non-speculum samples cannot be analysed (this is normally due to insufficient DNA) will be asked to collect another sample using the same method. Based on a previous self-sampling study we performed, we expect this will be in the region of 2% [24] of all returned samples. Women who had a non-speculum clinician collected sample will be asked to book an appointment for another clinician sample. Women who returned a self-sample will be sent another self-sampling kit with an accompanying letter. If the second sample is also inadequate the woman will be advised to make an appointment at her GP practice to have a routine cytology test taken.

5.7 Acceptability – participating patients

All women who have a non-speculum sample taken for HPV testing will be asked to complete an anonymous self-complete questionnaire to assess the acceptability of non-speculum sampling for HPV testing, and future screening preferences. Completed questionnaires will be handed back to GP practice staff (non-speculum clinician taken samples only) or posted to the study team (using a self-addressed postage paid envelope which will be provided).

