6 SAMPLE HANDLING

6.1 Non-speculum clinician collected samples

Study kits will be provided to the participating GP practices and will contain:

- Participant information sheet
- HPV information sheet
- Informed consent form
- Study patient questionnaire
- Flocked swab (Copan FLOQswab[™])
- Specimen bag

At the appointment the GP or nurse will collect a non-speculum vaginal sample using a flocked swab (Copan FLOQswab[™]). The flocked swab is approximately 12.5 cm long and comes in a tube with a re-sealable lid.

In order for the sample to be processed at the laboratory the sample will have a minimum of two patient identifiers (full name and date of birth) and an accompanying study lab request form.

Study lab request forms will have the following details:

- Full name
- Date of birth
- Address
- NHS number
- Name of sample taker
- GP Practice

An EMIS (the GP record software system) web mail-merge document will be set-up to enable printing of lab request forms that will be auto-populated with the relevant details.

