6.2 Self-sampling

Self-sampling kits will be posted to women by the study team and will contain:

- Participant information sheet
- Laboratory Request/ Consent Form
- HPV information sheet
- Instructions on how to take the sample (written and pictorial)
- A flocked swab (Copan FLOQswab[™]) in a tube with a re-sealable lid
- Study patient questionnaire (with a self-addressed postage paid envelope)
- A UN3373 compliant freepost envelope or box that is pre-addressed to the laboratory

The instructions enclosed with the kits will explain in detail how to take the self-sample and how to return it. The self-sample will be taken by the woman using the flocked swab which is approximately 12.5 cm long and comes in a tube with a re-sealable lid.

Study laboratory request/ consent form will include the following details:

- Date sample was taken
- Full name
- Date of birth
- Address
- Telephone numbers

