8.2 Planned analysis

The primary outcome measure is screening uptake at 4m in women offered non-speculum HPV testing vs women sent a cervical screening reminder letter. Secondary outcomes will be: (i) 12m coverage; and (ii) the acceptability of non-speculum clinician sampling in lapsedattenders aged 50-64.

We will also report: (i) the proportion of women who undergo clinician-taken sampling without a speculum versus the proportion who request and return a self-sample (ii) future screening preferences and (iii) the proportion of lapsed attenders who test HPV positive on a non-speculum sample and attend for (a) follow up (cytology or colposcopy) and (b) who are treated for CIN2+.

The Chi Squared test will be used to determine the differences in proportions between groups. For HPV positive women we will calculate the proportion who have a follow-up investigation within six months. Descriptive statistics will be used to compare demographic and cervical screening status between responders and non-responders.

A descriptive analysis of patient questionnaire data will be used to assess acceptability of each approach and intention to take part again in the future if invited.

A descriptive analysis of swab-taker questionnaire data will be used to assess the acceptability, experiences and practicalities of the non-speculum sampling from the clinicians' viewpoint.

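### Only clinician-sampled women may return the acceptability questionnaire to the practice that took the sample, with no requirement to seal it, and their kit list omits the return envelope

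*Protocol*

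**What the plan says.** Section 5.7 asks every woman who has a non-speculum sample to fill in an "anonymous self-complete questionnaire to assess the acceptability of non-speculum sampling for HPV testing, and future screening preferences". On return it says: "Completed questionnaires will be handed back to GP practice staff (non-speculum clinician taken samples only) or posted to the study team", and adds that a postage-paid envelope will be supplied. The words in brackets confine hand-back to clinician-sampled women, so self-samplers can only post.

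The two kit lists differ. Section 6.2 gives self-samplers a "Study patient questionnaire (with a self-addressed postage paid envelope"). Section 6.1 lists only a "Study patient questionnaire" for the clinician kit, with no envelope.

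The sample is taken at the same practice that may receive the form: "At the appointment the GP or nurse will collect a non-speculum vaginal sample using a flocked swab" (section 6.1). Section 4.2 describes the questionnaire as covering "non-speculum sampling (non-speculum clinician sampling and self-testing) and future screening preferences". Section 8.2 states its use: "A descriptive analysis of patient questionnaire data will be used to assess acceptability of each approach".

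**The concern.** A woman who hands in her form is giving her opinion of an intimate procedure to the organisation that carried it out, possibly to a colleague of the person who did it. Some women will soften a critical answer in that position. A self-sampler who posts her form to researchers is not under that pressure.

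Acceptability is part of the study aim (section 2.1). Patient questionnaire data are the endpoint for one of the secondary objectives in 2.3, and 8.2 names the acceptability of non-speculum clinician sampling as a secondary outcome. What is at stake is the descriptive rating of clinician sampling and the stated future preferences of the women who had it. Both could look somewhat better than they are, and few women are likely to supply the data.

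**Working it through.** The plan gives no figure for this bias, so there is none to reproduce. The check is a comparison of sections, followed by an illustration of scale.

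**Comparison of sections**

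| Item | Clinician-sampled | Self-sampled |
|---|---|---|
| Hand-back to practice staff (5.7) | allowed | not allowed |
| Post to study team (5.7) | can be read as allowed | the only route |
| Return envelope promised (5.7) | yes, if posting is open to all | yes |
| Return envelope in kit list (6.1, 6.2) | not listed | listed |
| Sealing of a handed-back form | not mentioned | not applicable |
| Anonymous and self-completed (5.7) | yes | yes |

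Two things follow. The routes are unequal by sampling method, and 5.7 and 6.1 do not agree on the envelope.

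**How many women**

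Table 1 (section 8.1) considers intervention-arm uptake of 8% to 16% among 350 women:

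- 350 × 0.08 = 28
- 350 × 0.16 = 56

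This is a planning range and not a ceiling. Section 8.1 also cites self-sampling response of up to 17.5% (350 × 0.175 ≈ 61). The number with a non-speculum sample would be lower if some of those screened attend for conventional screening. With an even split between methods (assumption), 14 to 28 women rate each method.

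**Possible size of the bias**

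Assumptions: true acceptability is 80% for both methods, so 20% of answers are unfavourable; a share *x* of unfavourable answers is softened when the form is handed back; a share *h* of clinician-sampled women hand it back.

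Spurious increase = 0.20 × *x* × *h*

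- *x* = 0.10, *h* = 1: 0.20 × 0.10 × 1 = 2 points
- *x* = 0.50, *h* = 1: 0.20 × 0.50 × 1 = 10 points
- *x* = 0.10, *h* = 0.5: 0.20 × 0.10 × 0.5 = 1 point
- *x* = 0.50, *h* = 0.5: 0.20 × 0.50 × 0.5 = 5 points

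**In proportion**

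One changed answer moves the result by 1/28 = 3.6 points to 1/14 = 7.1 points. The standard error of an 80% rating is √(0.8 × 0.2/28) = 7.6 points to √(0.8 × 0.2/14) = 10.7 points. The illustrated bias of 1 to 10 points is therefore at most about the size of one standard error. It differs from sampling error in having a predictable direction for the clinician-sampling rating, and in being avoidable.

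**The case against.** Much of the case on the other side stands.

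- **Open forms.** A reader might infer that women hand over an open form for staff to read. No section says that. The fair statement is that nothing requires the form to be sealed.
- **Hand-back as the default.** A reader might infer this from the missing envelope in 6.1. But 5.7 promises an envelope in a paragraph about all sampled women, and is naturally read as letting any of them post, with hand-back an added convenience. Nor does the 6.1 list cover everything used at the visit: the laboratory request form is absent from it too, because it is printed from the practice system. The omission is a drafting gap between two sections.
- **The comparison of methods.** A reader might conclude that the formal clinician-versus-self comparison is compromised. It is not. The objective that begins "To assess the acceptability of clinician-sampling" (section 2.3) has uptake proportions as its endpoint, which the return route cannot affect. No between-method test of questionnaire answers is specified.
- **Larger differences remain.** Women choose their own method, and the setting differs. A common envelope changes neither.
- **Size and net direction.** It is tempting to say that three softened answers would shift the result by 11 to 21 points (3/28 to 3/14), but three is arbitrary. At 80% acceptability only 14 × 0.20 = 2.8 to 28 × 0.20 = 5.6 unfavourable answers exist to be softened, so three would mean all or more than half of them. Postal return may also lose dissatisfied self-samplers, so the net direction of any contrast between methods is not established.
- **Response.** Hand-back probably helps the return rate, which matters with a few dozen women.

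These points limit the concern without removing it. Anonymity towards researchers is weaker protection towards the staff member who receives the form in person. The rating of clinician sampling is also of interest on its own, without any comparison.

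**Conclusion.** The point holds as a modest design weakness. Section 5.7 allows clinician-sampled women, and no others, to return their rating to the practice that took the sample, without asking that it be sealed. Section 6.1 omits the envelope that 5.7 promises and 6.2 lists. Together these allow courtesy bias in the acceptability and future-preference answers from clinician-sampled women.

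The size is unknown. The 1 to 10 points shown above rest on assumed values for true acceptability, softening and hand-back, none of which the protocol gives. Anonymity, self-completion and the option to post are partial safeguards. The primary endpoint, the sample size and the uptake-based clinician-versus-self endpoint are unaffected. Priority is low to moderate; the case for acting is that the remedy is nearly free.

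**What to change.** Make two edits.

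- **Section 6.1:** add to the clinician kit the same self-addressed, postage-paid questionnaire envelope that 6.2 lists.
- **Section 5.7:** state that every questionnaire reaches the study team sealed and unread, either posted by the woman or left sealed at the practice and forwarded unopened.

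This keeps the convenience of leaving the form at the practice while removing staff sight of the answers. The cost is one envelope per clinician kit, a few dozen at the uptake considered here, and possibly a slightly lower or slower return. No recalculation is needed. Because self-selection and setting still differ, any contrast between methods in the questionnaire answers should stay descriptive.
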